Institutional Review Board Intervention/Interaction Detailed Protocol

Principal Investigator: [name]

Project Title: Clinical and Patient-Reported Outcomes After Ultrasound-guided vs. Open Trigger Finger Release

Version Date: 6/6/2023

For Intervention/Interaction studies, submit a Detailed Protocol that includes the following sections. If information in a particular section is not applicable, omit and include the other relevant information.

1. Background and Significance

Trigger finger is initially treated conservatively. Conservative treatment options include modification of activities, painkiller administration, splinting, and corticosteroid injections (1). Open or minimally invasive surgical treatment can be considered if conservative treatment fails. Minimally invasive surgery options consist of ultrasound-guided or blind percutaneous trigger finger release.

Many studies have reported good clinical outcomes after ultrasound-guided trigger finger release, including low rates of catching or locking recurrence rates, high QuickDASH scores and high patient satisfaction (2-4).

Postoperative clinical outcomes of open surgery have been widely compared to percutaneous surgery (5-8). However, the comparison of postoperative results between ultrasound-guided and open trigger finger release has been scarcely reported. Nikolaou et al. reported that ultrasound-guided trigger finger release resulted in a significantly sooner return to normal activities and better patient-reported cosmetic outcomes than open trigger finger release (9). Success rates and mean QuickDASH scores did not differ significantly between these groups in this cohort.

The potential benefits of ultrasound-guided trigger finger release compared to open trigger finger release have yet to be investigated. This study aims to prospectively analyze patient-reported outcomes in patients undergoing open vs. ultrasound-guided trigger finger release.

2. Specific Aims and Objectives

This study aims to prospectively analyze clinical and patient-reported outcomes in patients undergoing open vs. ultrasound-guided trigger finger release. Patients will not be randomly assigned to one of these two groups; rather, they will undergo the type of trigger finger surgery that they already agreed to with their surgeon, and we will measure the outcomes. Because of this, the study does not change the patient's standard of care; we are simply looking to collect additional data points.

3. General Description of Study Design

Retrospective part

Patient characteristics and disease-related (trigger finger) variables will be collected retrospectively from patient charts on EPIC.

Prospective part

This will be a prospective two-arm study. Patients will either be treated with ultrasound-guided trigger finger release or open trigger finger release (conventional method). [name] is the only surgeon within the Mass General Brigham (MGB) hospitals that performs ultrasound-guided trigger finger release. All other surgeons perform open trigger finger releases.

Surgeons will measure range of motion and grip strength preoperatively and during postoperative visits, which is part of routine care. We will also administer questionnaires to see how patients are doing postoperatively. See the '6. Study Procedures' for a more elaborate description of the visits.

4. Subject Selection

Inclusion criteria:

1. ≥ 18 years of age
2. Clinical diagnosis of trigger finger
3. Patient has failed conservative treatment or elects not to undergo conservative treatment
4. Surgeon agrees that surgery is indicated
5. Subject agrees to complete follow-up questionnaires over a 6-month period

Exclusion criteria:

1. Prior surgery on the target finger
2. History of prior surgical pulley release in the target hand
3. History of prior surgical pulley release in the contralateral hand within 3 months of enrollment or with persistent symptoms that interfere with normal daily activities or work at the time of consent
4. Corticosteroid injection in the target finger or hand within 6 weeks of surgery
5. Presence of additional process in the target wrist or hand requiring additional intervention beyond pulley release (e.g., neurolysis, mass removal, tenosynovectomy)
6. Clinically significant trauma or deformity of the upper limb (shoulder to hand) on the target side
7. Clinically significant vascular disease (including Raynaud's phenomenon) of the upper limb (shoulder to hand) on the target side
8. Clinically significant neurological disorder (including complex regional pain syndrome) of the upper limb (shoulder to hand) on the target side
9. Planned surgical or interventional procedure on the contralateral wrist or hand

10. Systemic inflammatory disease (e.g., rheumatoid arthritis, lupus)
11. Amyloidosis
12. Diabetes not controlled by a stable dose of medication over the past three months
13. Pregnant or planning pregnancy in the next 6 months
14. Workers' compensation subjects
15. Inability to provide a legally acceptable Informed Consent Form and/or comply with all follow-up requirements, including patients who do not speak English
16. Subject has other medical, social, or psychological conditions that, in the opinion of the investigator, preclude them from receiving the pre-treatment, required treatment, and post-treatment procedures and evaluations.
17. Trigger Thumb

How individuals are identified for recruitment, including description of the use of recruitment materials such as flyers, brochures, advertisements, letters, etc.

We are selecting patients interested in undergoing surgical treatment for a trigger finger. Thus, these patients are being seen by a hand surgeon at one of the hospitals within the MGB system (MGH main campus, MGH MGH Waltham, MGH Danvers, BWH main campus, BWH Faulkner and BWH Foxborough) for a trigger finger.

Who is responsible (role on research team) for identifying and recruiting individuals

The orthopedic surgeons and study staff at one of the MGB hospitals (MGH main campus, MGH MGH Waltham, MGH Danvers, BWH main campus, BWH Faulkner, and BWH Foxborough).

When individuals are recruited

Individuals are recruited when indicated for trigger finger release at the outpatient clinic if eligible.

Where individuals are recruited

Patients are recruited at the outpatient clinic of one of the MGB hospitals (MGH main campus, MGH MGH Waltham, MGH Danvers, BWH main campus, BWH Faulkner, and BWH Foxborough).

How recruitment goals match the prevalence rates of the condition/disease being studied and the populations most impacted by the condition/disease being studied

Trigger finger release is a very common procedure to relieve symptoms of a trigger finger. Many patients get treatment for this disease within the MGB hospitals (MGH main campus, MGH MGH Waltham, MGH Danvers, BWH main campus, BWH Faulkner, and BWH Foxborough). The prevalence is higher in diabetic patients than in the general population (10, 11). The recruitment goals will match the prevalence rates of the condition as it is a very common disease, and many patients with comorbidities (i.e., diabetes, thyroid disease) receive treatment within the MGB hospitals (MGH main campus, MGH MGH Waltham, MGH Danvers, BWH main campus, BWH Faulkner and BWH Foxborough).

Methods to enhance enrollment of diverse individuals and under-represented populations

We will include all patients who meet the inclusion criteria. We do not exclude patients based on race, color, national origin, sex, sexual orientation, or religion. We will not enroll vulnerable patient populations in this study.

5. Subject Enrollment

Patients will be prescreened through retrospective manual chart review.

Patients will be contacted in person at one of the MGB hospitals (MGH main campus, MGH Waltham, MGH Danvers, BWH main campus, BWH Faulkner, and BWH Foxborough). Patients who meet the inclusion criteria will get a summary of the study by an orthopedic surgeon or a study staff member to see if they are interested. If patients are interested, they will receive the study fact sheet, and the surgeon or study staff member will explain the study in more detail and answer any questions the patient may have. Subjects will be asked to complete the questionnaire either in person or over email or telephone before surgery. Subjects who opt to not complete the questionnaire in person will be contacted using the email or telephone script approved in this study. Subjects who do not complete the pre-op questionnaire before surgery will be withdrawn. Subjects can opt to receive an encrypted or unencrypted email. Subjects who indicate verbally in the outpatient clinic that they do not wish to participate will not be included in the study.

Depending on the treating surgeon, patients will either be treated with an open trigger finger release or an ultrasound-guided trigger finger release.

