6. STUDY PROCEDURES

Study visits

Visits	Procedures
Visit 1 – before surgery	
- Obtain informed consent- ADL questionnaire (see next section)- Visual analog scale for pain (VAS): pain on a scale of 1 to 10 
The measurements are part of standard care and performed by caregivers
 
- Perform the following measurements: range of motion of the PIP joint of the affected finger (including noting any flexion contracture), distance fingertip to distal palmar crease (DPC), and grip strength using Jamar 2 setting.
Visit/Telephone call 2 (2-4 days after surgery)	
- Take the following questionnaire:
1. Are you able to return to activities of daily living, and what activities do you still have trouble doing? You can list the activities you are having trouble with.2. VAS3. How many oxycodone or other narcotic medications are you taking post-op4. Are you able to return to work?

	
5. Are you satisfied with the procedure, and would you choose to have it again for a similar problem?
 
- Take the ADL questionnaire (see next section)- If in person (part of standard care, only collected by study staff, measurements performed by caregivers): Perform the following measurements: range of motion of the PIP joint of the affected finger (including noting any flexion contracture), distance fingertip to distal palmar crease (DPC), and grip strength using Jamar 2 setting.
Visit/Telephone call 3 (6-8 days after surgery)	
- Take the following questionnaire:
1. Are you able to return to activities of daily living, and what activities do you still have trouble doing? You can list the activities you are having trouble with.2. VAS3. How many oxycodone or other narcotic medications are you taking post-op4. Are you able to return to work?5. Are you satisfied with the procedure, and would you choose to have it again for a similar problem?- Take the ADL questionnaire (see next section)- If in person (part of standard care, only collected by study staff, measurements performed by caregivers): Perform the following measurements: range of motion of the PIP joint of the affected finger (including noting any flexion contracture), distance fingertip to distal palmar crease (DPC), and grip strength using Jamar 2 setting.

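### Triggering grade, symptom duration and earlier treatment have no standard pre-operative field and are left to chart review, in a comparison where arm is fixed by surgeon

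*Combined protocol and SAP*

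**What the plan says.** All references are to the combined protocol and SAP.

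- **Allocation** (Specific Aims and Objectives): "Patients will not be randomly assigned to one of these two groups; rather, they will undergo the type of trigger finger surgery" they had already agreed with their surgeon.
- **Arm and surgeon** (General Description of Study Design): one surgeon "is the only surgeon within the Mass General Brigham (MGB) hospitals that performs ultrasound-guided trigger finger release", and "All other surgeons perform open trigger finger releases". Subject Enrollment confirms it: "Depending on the treating surgeon, patients will either be treated with an open trigger finger release or an ultrasound-guided trigger finger release".
- **Source of disease variables** (Retrospective part of the design): "Patient characteristics and disease-related (trigger finger) variables will be collected retrospectively from patient charts on EPIC". There is no item list, grading scale or abstraction rule.
- **Prior treatment** (Subject Selection): inclusion 3 reads "Patient has failed conservative treatment or elects not to undergo conservative treatment". Exclusion 4 bars a steroid injection only within 6 weeks of surgery, so earlier ones are allowed.
- **Prospective baseline** (Study Procedures, Visit 1): ADL questionnaire, pain VAS, PIP motion with any flexion contracture, fingertip-to-palmar-crease distance and grip. On the physical measures the design section says: "Surgeons will measure range of motion and grip strength preoperatively and during postoperative visits, which is part of routine care". A subject who does not complete the pre-operative questionnaire before surgery is withdrawn (Subject Enrollment).
- **Endpoints**: the five questions with the ADL questionnaire, and recurrence or incomplete release, are primary.
- **Analysis** (Statistical Analysis): t-tests, Mann-Whitney, Fisher or chi-squared tests. No covariate adjustment is described.

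**The concern.** In a non-randomised comparison the reader judges comparability from the baseline description and from any adjustment built on it. Four items that bear on prognosis appear neither at Visit 1 nor in the list of variables: how badly the finger triggers, how long it has done so, what injections it has had, and which limb of inclusion 3 applied. Chart review is the only stated route to them.

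Because surgeon and arm coincide, a difference in charting habits would become a difference between arms. A real imbalance could then look like balance, and adjustment on the charted value would remove too little of it. The gap is most direct for recurrence or incomplete release: this is a primary endpoint, and its pre-operative counterpart, triggering status, has no prospective record.

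**Working it through.** **Figures taken from the plan.** The design effect is 0.5 SD with 51 per group. The point does not depend on the sample size calculation; 51 per group is used only to express a bias as an error rate. (A one-sided t-test reproduces 51 per group, with power 0.806. A two-sided test would need 64. The plan does not state sidedness.)

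**Assumed inputs; none is in the documents.** True prevalence of severe triggering is pU = 30% (ultrasound) and pO = 50% (open). Severity worsens the outcome by g = 0.5 SD. There is no technique effect. A chart records a severe case with probability sU or sO and never records a mild case as severe.

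**Step 1, unadjusted bias.** g × (pO − pU) = 0.5 × (0.50 − 0.30) = 0.10 SD in favour of ultrasound. This is 0.10/0.5 = 20% of the design effect.

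**Step 2, bias left after adjusting for charted severity.** Among patients charted as not severe, the share truly severe is r = p(1 − s)/(1 − ps) in each arm. With w the average share charted as not severe, the remaining bias is g × w × (rO − rU).

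For sU = 0.9 and sO = 0.6:
- rU = 0.03/0.73 = 0.0411
- rO = 0.20/0.70 = 0.2857
- w = 1 − (0.27 + 0.30)/2 = 0.715
- remaining bias = 0.5 × 0.715 × 0.2446 = 0.087 SD

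| True severe, US / open | Chart sensitivity, US / open | Charted severe, US / open | Bias after adjustment (SD) |
|---|---|---|---|
| 30% / 50% | 0.90 / 0.90 | 27% / 45% | 0.016 |
| 30% / 50% | 0.90 / 0.80 | 27% / 40% | 0.042 |
| 30% / 50% | 0.90 / 0.70 | 27% / 35% | 0.065 |
| 30% / 50% | 0.90 / 0.60 | 27% / 30% | 0.087 |
| 30% / 50% | 0.90 / 0.54 | 27% / 27% | 0.100 |
| 30% / 50% | 0.60 / 0.90 | 18% / 45% | 0.019, opposite sign |
| 40% / 40% | 0.90 / 0.60 | 36% / 24% | 0.052 |

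In the fifth row the imbalance is invisible and adjustment removes none of it. In the sixth the gap is exaggerated and little bias remains. In the last there is no true imbalance, and adjustment creates a bias.

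**Step 3, effect on error rate.** With 51 per group and no true effect, a bias of 0.10 SD raises the two-sided type I error from 5% to 7.9%. A bias of 0.016 SD raises it to 5.1%.

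**Step 4, what the existing baseline scores could remove.** Suppose severity also shifts a baseline score by h SD, and the baseline and outcome scores correlate at ρ within severity groups. The mean within-arm variance of severity is v = (0.3×0.7 + 0.5×0.5)/2 = 0.23. Adjusting for the baseline score alone has slope β = (ρ + ghv)/(1 + h²v) and leaves (g − βh) × 0.20.

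- ρ = 0.5: 0.047 SD if h = 0.5; 0.017 SD if h = 0.8.
- ρ = 0.3: 0.066 SD and 0.045 SD.
- ρ = 0: 0.095 SD and 0.087 SD.

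**The case against.** The case for leaving the plan as it is has four parts.

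1. **Much of baseline severity is already prospective.** ADL and VAS are reported by the patient, required before surgery, and are baseline versions of primary endpoints. Motion, contracture, fingertip distance and grip are also measured. This stands: a reader might infer that all baseline severity comes from charts, and Visit 1 contradicts that. Step 4 shows that these scores can remove a good part of the bias under favourable assumptions. They do not say whether a finger catches, locks or is fixed, or what treatment has failed.

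2. **Differential charting is not shown.** A reader might infer that severity is in fact recorded differently in the two arms. The documents say who operates, not who writes the notes, and all charts are on one EPIC system. This stands: the text supports only the possibility. Calling these items the main confounders would also be a judgement, because the plan names no confounders.

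3. **The planned tests are unadjusted.** The adjustment figures above therefore describe an analysis that is not in the plan. In the 30%/50% example the planned estimate is off by 0.10 SD however good the charts are. This also stands. Until an adjusted comparison is added, the immediate cost is a baseline table that could mislead.

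4. **Some of it can be recovered.** Symptom duration, injections and declined treatment could be asked at a later contact, with recall error. That is fair for those items. A pre-operative triggering grade cannot be reliably reconstructed after the release.

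**Conclusion.** The point holds as a cheap improvement. The four items have no standard prospective field, chart review is their only stated source, and arm coincides with surgeon, so any difference in charting would fall along the comparison of interest.

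The size is unknown and probably modest. Under the assumed 30%/50% split worth 0.5 SD, 0.02 to 0.10 SD remains after adjustment, or roughly 4% to 20% of the design effect. The sign can reverse if the ultrasound charts are the less complete ones. These figures rest entirely on assumed prevalences, effect and sensitivities, and matter only once an adjusted analysis exists.

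The documents do not support the stronger conclusions that the arms' records do differ, that the comparison is biased by a known amount, or that the baseline scores already collected cannot help.

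**What to change.** Add about five fixed-choice fields, worded identically in both arms and completed before surgery:

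- triggering grade, recorded with the Visit 1 measurements;
- symptom duration;
- digit;
- number and date of earlier injections, including any given elsewhere;
- conservative treatment failed, or declined.

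The items a patient can answer fit the pre-operative questionnaire, which is already mandatory. The injection date would also document exclusion 4. Chart review can remain for demographics and comorbidity.

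Report these fields by arm. Include them, with baseline ADL and VAS, as covariates in a prespecified adjusted comparison presented beside the unadjusted tests in Statistical Analysis. Both parts are needed: new fields that no analysis uses change little, and adjustment on charted values alone is exposed to the problem described.

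The cost is a protocol amendment and a few minutes at an existing contact, with no added visit and no change to care. Patients already enrolled would have chart-derived values only, and these should be flagged in the data and in the report.

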We will use a student t-test to analyze normally distributed continuous data. When we compare data at two different time points within a group, we will use a paired student t-test. When we compare continuous data of two different groups, we will use an unpaired student t-test.

We will use a Mann-Whitney U test if the continuous data is not normally distributed.

We will use Fischer's exact test or a Chi-squared test for differences in categorical variables, depending on the number of events in the different groups.

Power analysis

We have performed a power analysis to find differences between two independent means (normally distributed) with alpha = 0.05, power = 0.80, and effect size 0.5. This would require a total sample size of 102 patients (51 in each group). If the data is non-normally distributed with the same alpha, power, and effect size, we would need a total of 106 patients (53 in each group).

This power analysis is performed for our most important primary outcomes: the 5-question and ADL questionnaires.

5. Monitoring and Quality Assurance

The full-time research coordinator and principal investigator are responsible for adherence to all IRB policies and guidelines and for the accuracy and completeness of all forms, entries, and informed consent.

Study data will be maintained in a locked filing cabinet and/or on password-protected computers. Questionnaires and self-reported responses will not become part of the subject's medical record. Hard copies of study-related data and forms will be stored in a lockable file cabinet. Only the investigators and study staff will have access to this information. Any magnetic or electronic information will be saved in password-protected computers, which only study staff members can access. REDCap, secure and HIPAA-compliant, will be used to collect all answers.

For guidance, refer to the following Partners policies:

Data and Safety Monitoring Plans and Quality Assurance

https://partnershealthcare-public.sharepoint.com/ClinicalResearch/DSMP_in_Human_Subjects_Research.pdf

Reporting Unanticipated Problems (including Adverse Events)

https://partnershealthcare-public.sharepoint.com/ClinicalResearch/Reporting_Unanticipated_Problems_including_Adverse_Events.pdf

6. Privacy and Confidentiality

- Study procedures will be conducted in a private setting
- Only data and/or specimens necessary for the conduct of the study will be collected

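### Technique is fully confounded with surgeon, and neither the planned tests nor the wording of the plan takes account of it

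*Combined protocol and SAP*

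**What the plan says.** Section 3 (General Description of Study Design) states that one surgeon "is the only surgeon within the Mass General Brigham (MGB) hospitals that performs ultrasound-guided trigger finger release" and continues: "All other surgeons perform open trigger finger releases". Section 5 (Subject Enrollment) makes surgeon the determinant of arm: "Depending on the treating surgeon, patients will either be treated with an open trigger finger release or an ultrasound-guided trigger finger release". Section 2 (Specific Aims and Objectives) confirms that "Patients will not be randomly assigned to one of these two groups".

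The Statistical Analysis section (numbered 4, after Benefits) says: "When we compare continuous data of two different groups, we will use an unpaired student t-test". It adds: "We will use a Mann-Whitney U test if the continuous data is not normally distributed". Categorical outcomes go to Fisher's exact or chi-squared tests. No surgeon, site or covariate term is planned. The power analysis is for two independent means, "with alpha = 0.05, power = 0.80, and effect size 0.5", giving 102 patients (51 per group), or 106 (53 per group) for non-normal data.

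The list of variables to be collected in section 6 (Study Procedures) does not include the operating surgeon. The Benefits section says the results are meant to support shared decision-making about the two techniques.

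**The concern.** The ultrasound mean contains the whole effect of one surgeon: skill, patient mix, site, counselling, prescribing habits, advice on returning to work. The open mean contains an average of such effects over several surgeons. The planned tests attribute the full difference to technique, with a standard error built from patient-to-patient variation only.

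Several primary endpoints could plausibly reflect a surgeon's practice as well as the technique, notably narcotic pills taken, return to work and satisfaction. For range of motion and grip strength, which are secondary, section 3 has surgeons take the measurements, so the measurer may differ by arm too.

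The stake is the meaning of the result. A patient elsewhere can choose the technique but not this surgeon. A significant difference may be an ordinary surgeon difference, and a null result may conceal a real benefit.

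**Working it through.** **1. The plan's own figure.** With noncentral-t power for two independent means, d = 0.5 and one-sided alpha 0.05, 51 per group gives 80.6% power, so 102 in total. For Mann-Whitney, with an effective sample size of n × 3/π, 53 per group gives 80.3%, so 106. Both stated figures reproduce, but only one-sided (two-sided needs 64 per group, 128 in total) and with fully independent patients, that is, a surgeon ICC of zero. Sidedness is a separate matter.

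**2. Inputs.**
- From the documents: 1 ultrasound surgeon, more than one open surgeon, n = 51 per arm, alpha 0.05.
- Assumed: k = 6 open surgeons with equal caseload, a continuous outcome with variance 1, a two-sided test, no technique effect, and an ICC from 0.001 to 0.10. The ICC is the share of outcome variance that lies between surgeons.

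**3. Surgeons as a random sample.**
- True variance of the arm difference: ICC × (1 + 1/k) + 2(1 − ICC)/n.
- Variance the t-test uses: (2/n) × the mean of the two expected within-arm variances. These are 1 − ICC (ultrasound) and (1 − ICC) + ICC × (n − n/k)/(n − 1) (open).
- Actual error: 2 × [1 − Φ(1.96 × √(test variance / true variance))].

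Worked at ICC 0.05:
- True variance: 0.05 × 7/6 + 2 × 0.95/51 = 0.0583 + 0.0373 = 0.0956.
- Test variance: the open-arm variance is 0.95 + 0.05 × 42.5/50 = 0.9925, the mean of 0.95 and 0.9925 is 0.97125, and × 2/51 this gives 0.0381.
- Ratio of standard errors: √(0.0956/0.0381) = 1.58.
- Error: 2 × [1 − Φ(1.24)], about 22%.

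| ICC (assumed) | True variance | Test variance | SE ratio | Actual two-sided error |
|---|---|---|---|---|
| 0.001 | 0.0403 | 0.0392 | 1.01 | 5.3% |
| 0.005 | 0.0449 | 0.0391 | 1.07 | 6.7% |
| 0.01 | 0.0505 | 0.0390 | 1.14 | 8.5% |
| 0.02 | 0.0618 | 0.0388 | 1.26 | 12% |
| 0.05 | 0.0956 | 0.0381 | 1.58 | 22% |
| 0.10 | 0.1520 | 0.0370 | 2.03 | 33% |

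Simulation (20,000 runs per setting) gave 8.4%, 12.0%, 20.8% and 33.0% for the last four rows. At ICC 0.05, 4 to 10 open surgeons give 23% to 21%. A one-sided 5% test, simulated with 5 open surgeons, gives about 15% at ICC 0.05.

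**4. More patients do not help.** As n grows, the variance cannot fall below ICC × (1 + 1/k). At ICC 0.05 and k = 6 that is 0.0583, a standard error of 0.24 SD with unlimited patients. The plan's test assumes √(2/51) = 0.20 SD at 51 per group.

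**5. Surgeons as fixed.** Here the problem is bias. With no technique effect, a gap of 0.2 SD between the ultrasound surgeon and the open average gives a significant two-sided result 17% of the time, and a gap of 0.3 SD gives 32%. The bias also works the other way: a true benefit of 0.5 SD with an adverse gap of 0.2 SD looks like 0.3 SD and is detected 32% of the time, against 70.6% without the gap (two-sided, 51 per group).

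**6. What a tipping-point analysis would show.** Take an observed difference of 0.5 SD with 51 per arm and k = 6. The usual variance is 2/51 = 0.0392, so z = 0.5/0.198 = 2.52. Significance is lost when 0.0392 + ICC × 7/6 exceeds (0.5/1.96)² = 0.0651, that is, at an ICC above (0.0651 − 0.0392) × 6/7, about 0.022.

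**The case against.** The design is openly disclosed: no randomisation, unchanged care, surgeon determines arm. No analysis can separate surgeon from technique when one arm has a single surgeon. All of that stands, and it is why the fix concerns recording, wording and sensitivity. Disclosing the allocation is still not the same as saying what it does to the comparison.

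A reader might infer that the trial's false-positive rate is in fact 22% or 33%. The documents do not support that. The ICC, the number of open surgeons and the equal caseload are all assumed, and at ICC 0.001 the inflation is negligible. The figures also cover continuous outcomes only. Recurrence and yes/no satisfaction face the same confounding but were not computed.

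A reader might also infer that the t-test is miscalibrated for any claim. It is not. For a conclusion confined to these particular surgeons, patient-to-patient variation is essentially the right error term. The inflated error belongs to a claim about technique in general. Nor does every difference between surgeons bias the result: differences among open surgeons alone add noise, and the bias comes from the gap between the ultrasound surgeon and their average.

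Finally, one might expect a random surgeon intercept, estimated in the open arm, to correct the standard error. It does not do so reliably. In simulation with 6 open surgeons at ICC 0.05, the surgeon variance is estimated as zero in about 36% of trials, and type I error is still about 11% with a 1.96 cut-off. A t reference on 5 degrees of freedom gives 5% there, but 0.7% at ICC 0 and 7% at ICC 0.10. It also rests on an untestable assumption that the sole ultrasound surgeon comes from the open surgeons' distribution.

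**Conclusion.** The concern holds as confounding of technique with surgeon that the plan neither acknowledges nor allows for. The direction of the error inflation for a claim about technique is certain, since any ICC above zero gives more than 5%. Its size is not: about 5.3% to 33% across assumed ICCs of 0.001 to 0.10, given 51 per arm, 6 open surgeons with equal caseload and a two-sided test of a continuous outcome.

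It would go too far to say that the trial will misreport a surgeon difference as a technique effect. No conclusion wording is prespecified. What the documents support is that nothing in the plan prevents it, while the stated use of the results, shared decision-making, invites it. The point should be addressed; it does not invalidate the study.

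**What to change.** 1. Add the operating surgeon to the variables collected in section 6.
2. State in the Statistical Analysis section that surgeon and technique cannot be separated in this design, and word the conclusion as ultrasound-guided release by one surgeon versus open release by other surgeons in this system.
3. Prespecify a sensitivity analysis that adds ICC × (1 + 1/number of open surgeons) × the outcome variance to the variance of the arm difference, over a range of assumed ICCs. State the assumption that the ultrasound surgeon is drawn from the same distribution as the open surgeons, and report the ICC at which significance is lost. Do not present a random-intercept estimate as a correction of the standard error.
4. If the ultrasound surgeon also performs open releases, which the documents do not say, report those separately.

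The cost is one recorded variable, one extra analysis and a sentence limiting the claim, with no change to care or recruitment. The price is a narrower conclusion and wider sensitivity intervals.
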